## VII. Study Procedures and Research Design

The UG3 phase is a proof-of-concept study to test mechanistic hypotheses of the acute effects of TBS on corticothalamic inhibitory control (IC) task-based functional connectivity (tbFC), IC task performance and ad lib smoking in the laboratory while preliminarily evaluating safety and tolerability of TBS among individuals with TUD. Clearly defined milestones, focused on iTBS

versus cTBS and baseline on IC circuitry, will be met before proceeding to Phase 2 (UH3), a 4-session (over 2-weeks) randomized iTBS versus cTBS trial to assess smoking behavior over two-weeks post-treatment period.

As shown in Fig. 1, individuals ( $N=30$ ) with TUD will complete a baseline MRI visit and, using a crossover design, be randomly assigned to receive iTBS on one visit and cTBS on the other visit. Following TBS, they will repeat the protocol and then perform the SRT [4]. The effects of TBS on IC brain and behavior and smoking on the SRT, along with safety and tolerability, will be assessed.

**Strategies to Ensure a Robust and Unbiased Approach.** As detailed throughout this section, the proposed study will achieve robust and unbiased results via several design features including: explicit inclusion/exclusion criteria; randomization and blinding; use of validated measures; explicit hypotheses and well-validated analytic strategies; power estimates; and careful consideration of potential confounds. As standard practice in our laboratory, we will maximize participant retention and data collection compliance, while maximizing fidelity by providing participants with training on all task procedures prior to data collection.

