*Figure 2. Individual variability in inhibitory control task-based r.IFG activation.* Randomly selected cases ( $n = 5$ ) from our pilot IC-task based fMRI-guided TBS study. Though all participants exhibited significant r.IFG activation in the IC-contrast image—similar to that reported in our prior published work [4: upper right excerpt], significant inter-subject variability in neuroanatomy along with variability in the foci of functional activation were identified above. Thus, an individual subject’s functional activity in their native space provides greater spatial specificity for targeting stimulation, as compared to using group mean activity following normalizing to an average template. *Landmarks for reference: \* = sinus; STG = Superior temporal gyrus.*

**Theta Burst Stimulation Protocols.** Following fMRI data preprocessing, modeling, ROI identification and verification (C.4.b) and setting up the neuronavigation protocol (C.4.c), participants will be randomized to receive TBS to the r.IFG on two separate experimental visits: iTBS on one visits; cTBS on one visit—counterbalanced across participants.

**Determining Resting Motor Threshold.** Standard procedures will be used to determine the participants resting motor threshold (RMT) using parameter estimation by sequential testing (PEST) procedures [53].

**Intermittent Theta Burst Stimulation (iTBS) to the r.IFG.** The total duration of the iTBS protocol [38] is 190 seconds. Participants will receive stimulation over the r.IFG (A series of 3-burst pulses presented at 5Hz, 10 pulses/sec, 10 pulses/train, 20 trains, 10.0 sec intertrain interval; 80% RMT, MagPro) using a figure 8 coil (Coil Cool B65 A/P). This protocol has been shown to enhance IC performance as shown in Figure 1.

**Continuous Theta Burst Stimulation (cTBS) to the r.IFG.** The total duration of the cTBS protocol [41] is 34 seconds. Participants will receive stimulation over the r.IFG (An intermittent series of 3-burst pulses presented at 6Hz, 18 pulses/sec, 600 pulses/train, .1 sec intertrain interval; 80% RMT, MagPro) using a figure 8 coil (Coil Cool B65 A/P). This protocol has been shown to reduced IC performance as shown in Figure 1.

**Randomization and Blinding.** This study utilizes a double-blind, crossover design with a counterbalanced (latin-square) [62] TBS condition order. Given the short—~1hr duration of the

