**Aim 1. Examine the effects of iTBS on IC neural circuitry and task performance.**

**Hypothesis 1:** As compared to baseline: r.IFG iTBS stimulation will strengthen corticothalamic tbFC and improve IC task performance; whereas r.IFG cTBS simulation will weaken corticothalamic tbFC and result in worse IC task performance. **Behavioral analysis plan:** Following procedures outlined in C.4.a, IC performance data will be analyzed with a repeated-measures ANOVA to examine the effects of Condition (Baseline, iTBS, cTBS). **fMRI data analysis plan:** Following procedures in C.4.b—C.4.d, IC corticothalamic tbFC will be processed and modeled using our validated strategy [4] and then Fisher-transformed correlation coefficients (rZ) scores for each participant during each condition will be fed forward and analyzed in SPSS using a repeated-measures ANOVA to examine the effect of Condition.

**Aim 2. Examine the effects of iTBS on ad lib smoking.** **Hypothesis 2:** As compared to baseline: r.IFG iTBS, will extend the duration of abstinence; whereas cTBS shorten the duration of abstinence during an ad lib smoking lapse paradigm in the lab. **Behavioral analysis plan:** As in [4], time to initiate ad lib smoking during the SRT (see C.4.a.2) will be analyzed in SPSS using a repeated-measures ANOVA to examine the effect of Condition. Main effects of Condition on secondary smoking topography variables (e.g. puff volume (ml) and number of puffs) will be explored.

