**Aim 3.** Examine safety and tolerability of administering r.IFG TBS. **Rationale.** Though TBS has a good safety profile [36, 37], prior studies assessment of tolerability and adverse events (AE's) have largely confined those assessments to the day of study [37]. In addition, although the TBS stimulation parameters proposed herein are published standards, the location—r.IFG for iTBS is novel and thus both acute and protracted (24 hrs. post-stimulation) safety and tolerability profiles need to be assessed. **Hypothesis 3:** r.IFG TBS will have a similar overall adverse event profile in a TUD population as previously observed in dorsolateral prefrontal cortex TMS trials. **Assessment Plan.** Participants will be administered the ROS questionnaire (see C.9) at the beginning and end of each TBS visit, and 24hrs. post TBS. [name] will oversee participant compliance and, in the event of an AE, consult with [name] who will serve as the Program Manager for AEs. Any AEs will be recorded in an AE log. If an AE is non-serious (self-limited with no intervention needed), no further action will be necessary. However, in the case of a serious, unresolved event, an AE follow-up log will be completed and subsequent safety procedures followed (see Human Subjects Section; DSMP). Treatment-emergent AEs for all participants and

comparisons between the number of participants with any adverse events will be conducted using Pearson's chi-squared test statistic.

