*fMRI Scan:* 1) a high-resolution anatomical scan; 2) a 7-minute run of the IC task (see Fig 1); and 3) a six minute resting state BOLD (blood-oxygen-level-dependent).

*Randomization:* This will be a single blind study where participants will be randomized 1:1 to receive one session of either intermittent TBS (iTBS) or continuous TBS (cTBS) following the first fMRI.

*SRT:* The Smoking Relapse task will be administered as described above.

*Experimental Visits 1 & 2:* At the beginning of each of these experimental visits, participants will first: provide an expired breath CO sample in order to assess recent smoking; and, among females, provide a urine sample in which the pregnancy test must be negative. Next, breath alcohol levels will be assessed with a handheld breathalyzer and participants must record a BAL of 0.0. If participants continue to be eligible after the biological samples, they will complete study questionnaires to assess mood and to characterize smoking-related behavior. After this, participants will move on to the first of two fMRI sessions followed by the TMS session and the second the fMRI and SRT task.

*fMRI Scan 1:* 1) a high-resolution anatomical scan; 2) a 7-minute run of the IC task (see Fig 1); and 3) a six minute resting state BOLD (blood-oxygen-level-dependent).

*TMS:* Upon randomization, participants will receive either iTBS or cTBS per the theta burst protocols described above.

*fMRI Scan 2:* 1) a high-resolution anatomical scan; 2) a 7-minute run of the IC task (see Fig 1); and 3) a six minute resting state BOLD (blood-oxygen-level-dependent). The second

*SRT:* The Smoking Relapse task will be administered as described above.

**Analytic Strategy** Behavioral and neural data analysis strategies are found in [1] and detailed below.

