## **XII. Data Safety Monitoring Plan**

This UG3 phase is a proof-of-concept study to test mechanistic hypotheses of the acute effects of theta bursts stimulation (TBS) on corticothalamic inhibitory control (IC) task-based functional connectivity (tbFC), IC task performance and ad lib smoking in the laboratory (smoking relapse task: SRT [4]), and while preliminarily evaluating safety and tolerability of TBS among individuals with TUD. Adults smokers meeting criteria for TUD (N =40) will complete a baseline MRI visit and, using a crossover design, be randomly assigned to receive iTBS on one visit and cTBS on the other visit. Following TBS, they will repeat the MRI protocol and then perform the SRT. The effects of TBS on IC brain and behavior and smoking on the SRT, along with safety and tolerability during each visit will be assessed.

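### Aim 3 tests any-AE counts with Pearson's chi-squared without naming the groups; if they are iTBS and cTBS, the data are paired and the test does not fit

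*Combined protocol and SAP*

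**What the plan says.** Section VII, Aim 3, Assessment Plan names one AE test: "comparisons between the number of participants with any adverse events will be conducted using Pearson's chi-squared test statistic". The sentence runs across a page break and reads awkwardly, and the groups are not named. No other AE test appears in the document.

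The design is a crossover. Under Theta Burst Stimulation Protocols, participants are "randomized to receive TBS to the r.IFG on two separate experimental visits: iTBS on one visits; cTBS on one visit". Section XII says they will, "using a crossover design, be randomly assigned to receive iTBS on one visit and cTBS on the other visit". The opening of Section VII and the paragraph on Randomization and Blinding agree. There is no sham or untreated arm.

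Tolerability is recorded around both stimulation visits: "Participants will be administered the ROS questionnaire (see C.9) at the beginning and end of each TBS visit, and 24hrs. post TBS". Each completer therefore has an any-AE result, yes or no, under each condition.

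For Aim 1 the plan treats condition as within person: "IC performance data will be analyzed with a repeated-measures ANOVA to examine the effects of Condition (Baseline, iTBS, cTBS"). Aim 2 uses the same model for time to smoking.

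Hypothesis 3 itself looks outside the trial: "r.IFG TBS will have a similar overall adverse event profile in a TUD population as previously observed in dorsolateral prefrontal cortex TMS trials".

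**The concern.** Pearson's chi-squared on a 2x2 table assumes that the two rows come from different people. Here an iTBS versus cTBS table would hold 60 entries from 30 people. The test uses only the two totals, so its p-value is the same whether the AEs fall in the same participants or in different ones. It discards the within-person information that a crossover collects, and its stated 5% level need not be its real level. If people prone to AEs report them after either type of stimulation, the correlation is positive and the test rejects too seldom. In a safety comparison that favours finding no difference. Aims 1 and 2 respect the pairing; Aim 3, as written, does not.

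**Working it through.** **Inputs from the documents.** 40 enrolled for 30 complete usable datasets (Section VI); alpha 0.05 (Section VII, Hypothesis Testing). A participant with unusable images may still have AE data from both visits, so the number of AE pairs could lie between 30 and 40. The plan gives no power, rate or margin for Aim 3, so there is no figure to reproduce. The only AE figure, headache in about 5% (Section VIII), is not an any-AE rate.

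**Assumed inputs.** Any-AE rates from 5% to 50%; latent (bivariate normal) within-person correlation from -0.5 to 0.7. At 30% rates, latent -0.5, 0 and 0.5 correspond to phi of -0.27, 0 and 0.32.

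**Why the level shifts.** With p1 and p2 the two rates, the variance of the paired difference is [p1(1-p1) + p2(1-p2) - 2·phi·√(p1(1-p1)p2(1-p2))]/n. Pearson's test omits the phi term. With equal rates, true variance divided by assumed variance is 1 - phi.
- phi = 0.32: the critical value 1.96 acts as 1.96/√0.68 = 2.38, giving a size of about 1.8%.
- phi = -0.27: 1.96/√1.27 = 1.74, giving about 8.2%.

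**Exact check.** All paired 2x2 tables were enumerated for n=30, with Pearson (no continuity correction) on the totals and mid-p McNemar on the discordant pairs. Entries are the % of trials that reject.

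| Assumed rates | Latent correlation | Pearson | Mid-p McNemar |
|---|---|---|---|
| 30% vs 30% | -0.5 | 8.0 | 4.8 |
| 30% vs 30% | 0 | 4.9 | 4.4 |
| 30% vs 30% | 0.5 | 1.8 | 4.0 |
| 10% vs 10% | 0.5 | 2.7 | 1.7 |
| 5% vs 5% | 0 | 2.8 | 0.8 |
| 50% vs 25% | 0 | 52 | 50 |
| 50% vs 25% | 0.5 | 52 | 64 |
| 50% vs 25% | 0.7 | 52 | 74 |
| 15% vs 5% | 0 to 0.7 | 26 to 21 | 18 |

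With 40 pairs, 50% versus 25% at correlation 0.5 gives 67% and 78%.

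**The paired interval at low rates.** The paired Newcombe 95% CI excludes zero in 1.7% of trials at equal 10% rates with correlation 0.5, and in about 18% at 15% versus 5%. Both match mid-p McNemar. At equal 5% rates with correlation 0 to 0.7 its coverage is 99.2 to 99.8%, so it is conservative there too.

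**Illustration.** Suppose AEs occur in 10 of 30 after one condition and 4 of 30 after the other. Pooled rate 14/60 = 0.233; chi-squared = 0.2²/(0.233 × 0.767 × 2/30) = 3.35; p = 0.067, whatever the overlap.
- No one with AEs under both: discordant pairs 10 and 4, mid-p 0.118, paired CI for the 20-point difference -4 to 42 points.
- All 4 with AEs under both: discordant pairs 6 and 0, mid-p = 2(1/64) - 1/64 = 0.016, paired CI 4 to 36 points.
- Unpaired CI: -2 to 40 points in both cases.

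**The case against.** The strongest reply is that the plan never says the test compares iTBS with cTBS. The only comparison stated in Aim 3 is with earlier DLPFC TMS trials; those are other people, so independence could hold. The text may also be incomplete, since Aim 3 points to a C.9 and a Human Subjects Section that do not appear under those labels. This stands: the paired fault is conditional, and what is certain is only that the comparison is not named. The external reading would still need reference counts that the document does not give.

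One sentence under Randomization could suggest separate groups: "participants will be randomized 1:1 to receive one session of either intermittent TBS (iTBS) or continuous TBS (cTBS) following the first fMRI". It does not rescue the test, because the visit descriptions that follow schedule stimulation at both experimental visits and the rest of the document describes a crossover.

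The effect may also be small. At zero correlation Pearson is near nominal. In the illustration, mid-p falls below 0.05 only with 3 or more people in common, while independence would predict 10 × 4/30 = 1.3. This stands too.

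A reader might infer that the paired interval restores the sensitivity lost at low AE rates. The calculation shows that it does not.

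**Conclusion.** The concern holds conditionally and is minor. If the comparison is iTBS versus cTBS, Pearson's independence assumption fails by design. Whether the test is then too conservative, about right or too liberal depends on rates and correlations that are assumed here. Moderate rates with positive correlation make it conservative and cost power; zero correlation leaves it near 5%; negative correlation inflates its size.

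Two stronger readings are not supported. One is that the plan will certainly hide a tolerability difference: the groups are not named, the direction is not fixed, and AEs are logged whatever the test. The other is that a non-significant result here will establish Hypothesis 3 or open the UH3 phase: no section makes this the test of Hypothesis 3 or links its p-value to the milestones, and Section VII describes the work as "preliminarily evaluating safety and tolerability of TBS among individuals with TUD".

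The missing DLPFC reference rate and criterion for similarity is a separate request to clarify, and does not add to the weight of this point.

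**What to change.** State in Aim 3 that the comparison is iTBS versus cTBS within participant, if that is the intent. Replace Pearson's test with mid-p McNemar, and report the paired difference in any-AE proportions with a 95% CI (paired Newcombe). The interval is there because it respects the pairing and shows how large a difference the data allow, not because it gains sensitivity when AEs are rare. If another comparison is meant, name it and the source of its counts.

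The change takes one or two sentences and no new data. Its costs:
- If AEs are rare, the paired test and interval detect less than Pearson (15% versus 5%, 30 pairs: about 18% against 21 to 26%).
- At zero correlation the paired test is slightly less powerful even at moderate rates (50% versus 25%: 50% against 52%).
- Participants with only one stimulation visit drop out of the paired analysis; their AEs should still be listed by condition.

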**Exploratory Aims.** *MRS Rationale.* Converging evidence supports changes in glutamate release as a likely molecular mechanism associated with synaptic plasticity [64]. Glutamate receptors are necessary for the initiation and expression of LTP and LTD and GABA receptors are involved in the modulation of these phenomena. Consistent with animal findings [65], proton MRS studies have demonstrated TUD is associated with abnormal medial prefrontal [66] and thalamic [67] concentrations of glutamate along with evidence for medial prefrontal GABA disturbances being associated with attentional bias to drug cues [68]. Emerging evidence suggests that LTP-like TMS to l.dIPFC is associated with increases in localized glutamate concentrations in depressed [69, 70] and healthy [71] individuals. Recent research has also demonstrated that LTD-like cTBS to motor cortex is associated with increases in localized GABA concentrations [72]. However, to the best of our knowledge, no studies have investigated the impact of TBS on r.IFG GABA or glutamate concentrations or the impact of TBS on localized neurometabolites in TUD. We posit that r.IFG TBS induced neurochemical changes may subsequently correspond with changes in IC.

[figure not shown]

Figure 3. Sample r.IFG voxel placement (top panel), sample fitted GSH (bottom-left), GABA / Glx (bottom-right) and Water / Creatine (bottom-center) spectra acquired with HERMES.

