**Data acquisition:** At each visit, the MRS acquisition voxel ( $25 \times 25 \times 30 \text{ mm}^3$ ) will be placed in the r.IFG to correspond to the brain tissue directly underneath the TMS coil (Fig. 3). Following placement of 6 saturation bands parallel to the voxel faces and auto-shimming, single-voxel water-suppressed  $^1\text{H}$ -MRS spectra will be acquired via HERMES (TR=2000ms; TE=80ms; number of averages=320) using editing pulse frequencies for GABA and GSH acquisition (1.9 [ON GABA], 4.56 [ON GSH], and 7.5 ppm [OFF] [73]; and a PRESS sequence maximally sensitive to glutamate (TR=2000ms; TE=40ms; number of averages=128 [74]. Unsuppressed water spectra will be acquired for each sequence. **Data analysis:** Skull stripping and whole brain tissue-type segmentation will be performed on MP-RAGE images using FMRIB software [75]. In-house MATLAB functions will be used to extract the 3D volume corresponding to the positioned MRS voxel to obtain within-voxel gray matter (GM), white matter (WM) and cerebrospinal fluid (CSF) tissue content for each subject. GM/WM ratios will be used as covariates in all statistical analyses. Eddy currents and residual water will be removed using in-house MATLAB functions. HERMES data will be analyzed using the Gannet MATLAB toolbox [76]. PRESS data will be analyzed using LCModel 6.3 [77]. Metabolites with fitting uncertainties  $<20\%$  will be retained.

Water will be quantified from a Gaussian-Lorentzian fit to the non-water-suppressed data. Within-voxel tissue fractions of gray and white matter and cerebrospinal fluid will be calculated based on automated segmentation in SPM 12 using a volume mask generated in Gannet [78]. Metabolite concentrations will be normalized to unsuppressed water and corrected for within-voxel CSF fraction. Cramer-Rao Lower Bound (CRLB) values will be provided by the ProFit software and only estimates with CRLB values < 20% will be submitted to further analysis. Estimated metabolite peak areas will be normalized to the unsuppressed water signal. Finally, metabolite/water, along with metabolite/creatinine, ratios will be corrected for within-voxel CSF fraction [79]. Glutamate, glutamine, and GABA ratios will be entered into HLM models with a priori contrasts to examine differences in metabolite concentrations following r.IFG iTBS vs cTBS and baseline. Associations between metabolite concentrations and corticothalamic tbFC, IC and smoking on the SRT will be examined.

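### The 20% percentage-error filter on MRS values selects on the concentration itself and can attenuate the exploratory TBS contrasts; the source of the CRLBs also needs reconciling

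*Combined protocol and SAP*

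**What the plan says.** The MRS analysis is described under Exploratory Aims in Section VII, in the data analysis text. Software is assigned by sequence: "HERMES data will be analyzed using the Gannet MATLAB toolbox" and "PRESS data will be analyzed using LCModel 6.3". Immediately afterwards comes a first retention rule, which keeps "Metabolites with fitting uncertainties" below 20% and names no further software. Later in the same text a second rule says that CRLB "values will be provided by the ProFit software and only estimates with CRLB values < 20% will be submitted to further analysis". ProFit appears nowhere else in the document, and no dataset is assigned to it.

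The retained values are the outcomes: "Glutamate, glutamine, and GABA ratios will be entered into HLM models with a priori contrasts", in order to "examine differences in metabolite concentrations following r.IFG iTBS vs cTBS and baseline". The same values are then related to connectivity, task performance and smoking on the SRT.

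The plan gives no expected CRLB, no expected loss, no other spectral-quality criterion for retention and no analysis without the filter. The Missing Data and Attrition text in Section VII covers prevention only.

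**The concern.** A quality filter should remove bad spectra whatever concentration they show. A percentage error mixes the two. Of two spectra with the same absolute uncertainty, the one with the lower concentration has the higher percentage and is the one removed. If TBS changes the concentration, the condition with the lower mean loses more of its low values. Its retained mean is pulled up more than that of the comparison condition, and the contrast moves towards zero.

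The HLM does not repair this. A likelihood-based mixed model copes with missing values when the gaps can be explained by what remains in the data. Here the gap depends on the value that was removed.

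At stake are the exploratory metabolite contrasts and the planned associations that use the same values.

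The ProFit sentence raises a separate problem. It leaves unclear which program's uncertainty decides whether a value enters the analysis.

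**Working it through.** **No figure to reproduce.** The plan states no MRS effect size, SD, CRLB or loss rate. Taken from the document: the 20% limit, the three metabolites, the three within-person conditions and 30 usable datasets (Section VI). Assumed: mean concentration 1, between-person SD 0.12, within-person SD 0.08, a 10% TBS effect per condition, and absolute error s between 5% and 18% of the mean.

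**Step 1, algebra.** With estimate c and absolute error s, s/c < 0.20 is the same as c > 5s. For s of 5%, 10%, 15% and 18% of the mean, values below 25%, 50%, 75% and 90% of the mean are dropped.

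**Step 2, one worked case.** Take s = 0.15 in every scan, so the cut-off is 0.75. Total SD = √(0.12² + 0.08²) = 0.144. The proportion lost is 1 − Φ(z) and the retained mean is m + SD·φ(z)/Φ(z), with z = (m − 0.75)/SD.

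- Baseline, m = 1.0: z = 1.73, 4.1% lost, retained mean 1.013.
- After a 10% fall, m = 0.9: z = 1.04, 14.9% lost, retained mean 0.939.
- After a 10% rise, m = 1.1: z = 2.43, 0.8% lost, retained mean 1.103.

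A true change of −0.100 is estimated as 0.939 − 1.013 = −0.074, and a true +0.100 as 1.103 − 1.013 = +0.090. Restricting to complete pairs gives −0.091 and +0.097. At s = 0.18 a true −0.100 becomes −0.045 (available values) or −0.076 (complete pairs). At s of 10% or less, loss of values is at most about 3% and shrinkage at most about 4%.

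**Step 3, the planned type of model.** A random-intercept model was simulated with 30 people and three conditions, one TBS condition raised by 10% and the other lowered by 10%, so the true iTBS-cTBS difference is 0.20. With all fits kept it returns 0.199 to 0.204. Shrinkage relative to the unfiltered result:

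| Typical error | Cut-off 5s | Same noise in every scan | Noise varying between scans (log-SD 0.25) | Range over assumptions |
|---|---|---|---|---|
| 8% | 0.40 | none | 0.3% | 0-4% (10% or less) |
| 12% | 0.60 | 1% | 2% | 1-5% |
| 15% | 0.75 | 10% | 6% | 6-25% |
| 18% | 0.90 | 28% | 10% | 10-45% |

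The last column allows less favourable assumptions within the same kind of model. A fall against baseline, for example, loses more than a rise. These columns apply the rule to the concentration without adding fitting scatter to it. Adding scatter increases the loss, so the ranges are illustrations and not limits.

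**Step 4, the alternative rule.** An absolute limit of s < 0.20 × baseline mean does not involve the session's own concentration. With a median error of 0.15 and log-SD 0.25, the proportion kept is Φ(ln(0.20/0.15)/0.25) = Φ(1.15) = 87.5% in both conditions. Under the percentage rule about 80% and 70% were kept for means of 1.0 and 0.9. The simulated difference under the absolute limit was the true 0.100.

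**Step 5, software.** HERMES is assigned to Gannet and PRESS to LCModel 6.3. The CRLBs are attributed to ProFit, which fits neither dataset.

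**The case against.** The strongest reply is that nothing in the document shows the filter would bite. The plan specifies 320 averages for HERMES, 128 for PRESS and a 25 × 25 × 30 mm voxel, and it describes the PRESS sequence as chosen for glutamate sensitivity. If typical errors are 10% or less, the bias is negligible. The rationale also points to increases: LTP-like TMS "is associated with increases in localized glutamate concentrations in depressed" and healthy people, and "LTD-like cTBS to motor cortex is associated with increases in localized GABA concentrations". An increase against baseline is truncated less than a decrease. Where scan quality varies, part of the filtering is on quality, as intended, and the loss is smaller. All of this stands, and it is why the size can only be given conditionally.

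A reader might infer that the effect will shrink by a third or a half. An unpaired comparison with the same noise in every scan, fitting scatter added and a 10% fall does lose 6-14% at a typical error of 12%, about 31% at 15% and about half at 18%. The documents do not support those as headline figures. They give no CRLB, they plan within-person contrasts, and their rationale cites rises.

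A reader might also infer that the filter cannot be run at all. That is too strong. The first statement of the rule can be applied with Gannet and LCModel, so the ProFit sentence is an inconsistency to reconcile.

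Two parts of the concern survive the reply. The dependence on concentration is algebra, and the plan contains nothing from which the sponsor could show the filter to be harmless.

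**Conclusion.** The point holds in a limited form. The 20% rule selects on the MRS outcome. When noise is similar across visits it can attenuate the iTBS, cTBS and baseline contrasts. The size runs from about nil at a typical error of 10% or less to about 6-25% at 15% and 10-45% at 18%, on the assumed SDs, effect size and noise described above. The metabolite with the poorest fit is most exposed, and glutamine is among the planned outcomes as well as glutamate and GABA. If noise differed by condition, the bias need not be towards zero; this was reasoned and not simulated.

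The outcome is exploratory, so Aims 1-3 are not affected. The two statements of the rule also disagree on the source of the uncertainty and must be reconciled. Severity: minor.

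**What to change.** State one retention rule in place of the two:

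- Keep an estimate if its absolute uncertainty (the reported percentage times the estimate) is below 20% of the group-mean baseline concentration of that metabolite, with the same limit for every session. Compute the baseline mean from all baseline fits, in the units that are analysed.
- Take the uncertainty from Gannet for HERMES and from LCModel for PRESS, and delete ProFit.
- Report the number of values excluded, by metabolite and condition.
- Repeat the HLM with all fits kept, as a sensitivity analysis. The values already exist, so no further data are needed.

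The cost is a change of wording in the analysis plan and one extra model run per metabolite. The downside is that a few noisier low values stay in the main model.
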